#### Questionnaires:

All participants will be asked to complete questionnaires described below. Questionnaires are validated and have been used successfully in prior SCI and SDB research. The RA will hand out the

questionnaires and allow the participant to complete them in a private setting. The RA will be available to answer any questions that may arise and will check the returned questionnaires for completeness. All questionnaires are found in Appendix 10.

### ***Sleep Questionnaires***

1) Sleep Quality (SQ): We will assess sleep quality using the Pittsburgh Sleep Quality Index (PSQI). The PSQI is the most widely used global sleep assessment tool. Validity and test-retest reliability of this instrument has been extensively studied. A global PSQI score greater than 5 yields a diagnostic sensitivity of 89.6% and specificity of 86.5% (kappa = 0.75, p < 0.001) in distinguishing 'good' and 'poor' sleepers.

[figure not shown]
2) Chronic Insomnia: We will use the Athens Insomnia Scale (AIS) to assess insomnia in the study population. It consists of eight items: the first five pertain to sleep induction, awakenings during the night, final awakening, total sleep duration, and sleep quality; while the last three items refer to well-being, functioning capacity, and sleepiness during the day. Reliability and validity for the instrument have been well documented.

3) Screening for SDB: We will screen for increased risk of SDB using the Berlin questionnaire (BQ). This is a validated questionnaire with good performance characteristics in the general population. It has been successfully used by our group in the SCI population (see preliminary data).

4) Daytime Sleepiness: Epworth Sleepiness Score (ESS) is a valid measure of subjective daytime sleepiness. Eight items are rated on a scale of 0–3, total scores range 0–24, with higher scores indicating a greater propensity to fall asleep in different situations. In samples of sleep apnea patients, it shows high internal consistency and correlates well with objective measures of sleep latency. It has successfully been used in SCI individuals.

5) Impact of Sleepiness on Functioning: The Functional Outcomes of Sleep Questionnaire (FOSQ) is the gold-standard, disease specific instrument designed to assess the impact of sleepiness on the ability to conduct daily activities. The FOSQ has proven validity and reliability, and is sensitive to treatment changes. There are 30 items, which are divided into 5 scales: Activity, Vigilance, General Productivity, Social Outcome, and Intimacy and Sexual Relationships. These scales are summed to make a total score. Higher scores on the FOSQ indicate self-perceived better daily functioning. The FOSQ has been used by our team in a previous study of acute SCI and sleep disorders.

**Figure 2. Study Flow and Measurements**

### **Mood, Pain, and Quality of Life Questionnaires**

1) Health related quality of life (HRQOL): We will measure HRQOL in participants using the Medical Outcomes Study Short Form SF-36 (v2, Quality Metric, Inc.). We will score tests online, and express results as the coalesced scores for physical and mental domains. The SF-36 is the most widely used of the HRQOL instruments, and has been used in populations of persons with SCI, and those with a wide range of sleep disorders. The instrument tests 8 coalesced dimensions of health that create a physical component score and a mental component score. Additionally, we will

use the recently proposed International SCI Quality of Life (QoL) Basic data set to facilitate future comparisons to other QoL studies in SCI worldwide. The QoL data set consists of 3 variables: ratings of satisfaction with general quality of life, satisfaction with physical health, and satisfaction with psychological health. All variables are rated on a scale ranging from 0 (completely dissatisfied) to 10 (completely satisfied).

2) Depression and Anxiety: A) Beck Depression Inventory-2nd edition (BDI-II): is a brief psychological screening tool to assess depressive symptomatology. The BDI-II is a 21-item, self-report measure with high test-retest reliability and internal consistency in a variety of patient groups, including those with SCI. It has been shown to correlate with biological markers of depression and to be sensitive to change. B) State-Trait Anxiety Inventory (STAI): The State-Trait Anxiety Inventory is a well-validated and reliable instrument that has been successfully used with SCI populations to evaluate anxiety.

3) Assessment of Pain: Presence and severity of pain will be determined by the *International Spinal Cord Injury Basic Pain Data Set (ISCIBPDS)* recently validated in persons with SCI. Additionally, in accordance with IMPACT II consensus recommendations for evaluating pain outcomes in clinical studies, we will determine the presence and severity of pain by a written numerical scale. Ranging from 0 to 10, with 0 meaning 'No pain' and 10 meaning 'Pain as bad as you can imagine,' the scale will be accompanied by the instructions, "Please rate your pain by indicating the number that best describes your pain on average in the last week." We will also use a verbal rating scale to measure pain intensity over the preceding week (none, mild, moderate, severe) as a secondary pain outcome measure.

Polysomnography: We will conduct portable in home Level II PSG in accordance with standards established by the AASM. We will use the *Embletta x100* portable recording unit. The PSG recording montage consists of two electroencephalographic channels (EEG-C3 and C4), left or right electrooculogram (EOG), chin muscle electromyogram (EMG), nasal cannula (NP-measure of airflow), thoracic and abdominal respiratory effort bands, body-position sensor, and pulse oximetry. The trained RA will connect participants to the device in the outpatient clinic or inpatient room. The *Embletta x100* will record overnight events. We will teach the participant and/or caregiver how to disconnect from the device prior to returning it to the clinic the following day. Portable sleep studies have been successfully used in outpatient clinical and research settings. The *Embletta x100* unit has been validated against a standard in laboratory, attended PSG with good performance characteristics and accuracy in detecting SDB.

A certified sleep technologist will perform manual scoring using 30 second epochs and standardized scoring techniques recommended by AASM. Drs. [name] and [name] will review all scored epochs and interpret the overall sleep study. PSGs performed by Detroit sites will be scored and interpreted centrally in Miami.

**Specific Aim 1: Determine the associations between sleep disordered breathing (SDB) and cognitive impairments in chronic SCI and the impact of PAP therapy on cognitive measures in a cohort with chronic SCI and SDB.**

**Protocol:** [name] will train RAs at both sites to perform a battery of comprehensive, cognitive assessments to obtain a global evaluation of cognitive functioning in all subjects with SCI who undergo PSG. The particular emphasis is on measures related to cognitive impairment common in persons with SDB. Administration of these tests by appropriately trained RAs is consistent with current standards of practice in clinical neuropsychology. Sample protocol sheets and stimuli for each cognitive measure can be found in Appendix 10.

**1) Pre-morbid Functioning:**

WIDE RANGE ACHIEVEMENT TEST – IV (READING SUBTEST): The WRAT-IV Reading Subtest is a norm-referenced test that measures the basic academic skill of word reading. It was standardized on a representative national sample of over 3,000 individuals ranging in age from 5 to 94 years. Higher scores are indicative of better sight reading abilities and can serve as a proxy for pre-morbid intellectual functioning.

2) Simple and Divided Attention:

a) DIGIT SPAN SUBTEST OF THE WECHSLER ADULT INTELLIGENCE SCALE –IV: The digit span subtest requires the individual to repeat a series of numbers in the same order, or in reverse order, than orally provided by the test administrator. Low scores on the digit span subtest suggest limited attention, while higher scores indicate a greater ability to concentrate and attend to orally presented information.

b) PACED SERIAL ADDITION TEST (PASAT): The PASAT measures divided, attention and working memory; cognitive domains that have been shown to be particularly salient to SDB. The individual being tested is given single digits at fixed intervals administered by a computer, and needs to add the current number to the last number on each successive presentation. The participant provides verbal responses and the examiner records the responses on a scoring sheet. Lower scores indicate greater impairment of attention.  **The PASAT is the primary outcome measure for this study.**

3) Processing Speed:

SYMBOL DIGIT MODALITIES TEST (SDMT): The SDMT is a substitution task that requires the individual being evaluated to replace symbols with the numbers assigned to them on a reference key. A time limit is imposed to complete the task. Only the oral version of the SDMT will be administered requiring verbal responses. The SDMT has shown excellent reliability, sensitivity, and validity.

4) Memory:

HOPKINS VERBAL LEARNING TEST-REVISED (HVLT-R): The HVLT-R is an assessment of verbal learning and memory, composed of three learning trials, a delayed recall trial, and a delayed recognition trial. It has high test-retest reliability and validity, and has been used in studies of participants with chronic medical conditions. 

5) Executive Function:

WISCONSIN CARD SORTING TEST-64 (WCST): The WCST-64 is used primarily to assess perseveration and abstract thinking. It is considered a measure of executive function because of its reported sensitivity to frontal lobe dysfunction. As such, the WCST allows the clinician to assess strategic planning, organized searching, and the ability to utilize environmental feedback to shift cognitive sets and direct behavior toward achieving a goal. The test is administered by computer. Participants will indicate their response verbally and the examiner will select the appropriate choice on the computer so that motor responses are not required.

This battery of tests takes approximately 75 minutes for subjects to complete. All cognitive measures will be completed at baseline and four month follow-up. Scoring of cognitive measures from Miami and Detroit sites will be completed by [name] at Miami site who will be blinded to study arm assignment.

**Specific Aim 2: Determine the impact of PAP therapy on surrogate CV biomarkers, sleep quality, quality of life, mood, and pain in a cohort with chronic SCI and SDB.**

Given the increased prevalence of CVD and its associated morbidity, mortality and health costs in the SCI population, much attention has been paid in recent years to identifying and modifying traditional and nontraditional CVD risk factors in SCI. SDB is likely to be a nontraditional, but

modifiable risk factor. Our study will be the first to evaluate in persons with chronic SCI, the association between SDB and surrogate cardiovascular biomarkers and the impact of PAP therapy on these measures.

### **Biomarkers**

We will measure inflammatory cytokines (TNF- $\alpha$  and hs-CRP), a cellular adhesion molecule (VCAM-1), a marker of oxidative stress (urinary 8-isoprostanate), and adiponectin at baseline prior to PAP intervention and at four month follow-up.

### ***Blood collection and sample preparation***

Participants will be instructed to refrain from caffeine and alcohol intake for 24 hours before testing. Antecubital venous blood samples will be taken under antiseptic conditions in the post-absorptive state after an overnight (10h) fast, and will be drawn between 8:00 and 10:00 am. Ten milliliters of fasting blood will be obtained in EDTA-containing vacutainer tubes or clot lysis activator tubes and centrifuged for 20 minutes at 1200 x g to obtain platelet poor plasma or serum, respectively.

After centrifugation, the serum or plasma are transferred to a new labeled tube and kept on ice or at 4°C until aliquots are prepared for storage. If multiple tubes are needed to obtain the requisite volume of sample, then samples from individual tubes will be pooled prior to preparation of sample aliquots. For freezing, aliquots of serum, plasma or urine will be added to appropriately labeled and identified cryogenic vials suitable for storage at ultra-low temperatures on the day of sample collection. Tube size will be dictated by the required sample volume. Sample vials will be placed in containers and frozen at  $\leq$  -70°C until shipped to the laboratory for analysis. Samples to be shipped frozen will be placed in approved Styrofoam shipping containers containing sufficient quantities of dry ice to maintain samples in a frozen state for at least 48 hours and sent by overnight courier.

### ***Urine Collection***

First morning urine specimens will be collected at home by participants. Participants will be instructed to collect as much as possible of first morning urine into the supplied container, place the lid on the container carefully and tightly and bring the specimen as soon as possible on the same day to the RA. For those participants who self-catheterize, urine specimens can be collected from catheters (e.g. Foley catheter) using a syringe, followed by transfer to a specimen tube or cup. We will normalize urinary 8-isoprostanate measurements to urinary creatinine levels to account for differences in dilution.

### ***Biochemical Assays***

**Quality control procedures:** For all quantitative metabolic and biomarker measures, the laboratory follows guidelines established by the Clinical Laboratory Improvement Act (CLIA) for quality control and proficiency testing. Each assay run must meet established quality control guidelines before results are accepted and reported. Sufficient stocks of control lots are maintained for long-term monitoring of assay precision and monitoring of long-term drift.

**Clinical Laboratory and Biomarker Testing:** Chemistry and immunoelectro-chemiluminescence (IECL) assays are performed by automated analyzer on a Roche Cobas 6000 analyzer following all manufacturer's instructions for instrument maintenance and assay calibration and test procedures. ELISA testing is performed by manual methods.

Assays, methodology, intra-assay CV (coefficient of variability), sample type and minimal sample requirements are shown in Table 1.

**Table 1: Assay method, sample type and volume requirement by test**

Test	Methodology	Assay CV	Reagent Manufacturer	Sample Requirement
C-reactive Protein	IECL	2.3%	Roche	0.3 ml Serum
Adiponectin	ELISA	4.7%	Mercodia	0.1 ml Serum
soluble VCAM	ELISA	5.8%	R&D Systems	0.2 ml EDTA Plasma
TNF-alpha (high sensitivity)	ELISA	6.2%	R&D Systems	0.5ml EDTA Plasma
Urinary 8-isoprostanate	ELISA	6.9%	Northwest Life Science Specialties	0.5 ml First Void Urine
Urine Creatinine (to normalize 8-Isoprostanate)	Chemistry	2.1%	Roche	0.5 ml First Void Urine

### Sleep, Quality of Life, and Mood

Sleep quality, quality of life, mood and pain will be evaluated at baseline and four months follow-up in each study arm using questionnaires, according to methodology described above.

### **Data Analysis:**

Feasibility: The SCI Service at Miami VA actively serves approximately 300 patients. The Miami Project maintains a database of persons who have volunteered their participation in research studies and a database of individuals who have participated in past studies and volunteered additional participation. The database currently contains 3400 persons whose ages and levels of injury match the sought study participants. The Detroit VA SCI service oversees the care of greater than 100 patients/year. The Rehabilitation Institute of Michigan provides care for 350 SCI individuals. We anticipate completion of enrollment by the second quarter of Year 4, with 100 patients enrolled for PSG from each site.

Sample size justification and power: We will recruit 200 participants who meet our eligibility criteria and anticipate an SDB prevalence of 0.50 in SCI participants. This will allow us to randomize 100 participants with SDB to PAP or placebo arm. The neurocognitive test best characterized in both SCI and SDB is the Paced Serial Addition Test (PASAT). The PASAT is our primary study outcome. A mean difference in PASAT scores of 7 discriminates between those with and without cognitive impairment in populations with and without SDB. Assuming a standard deviation of 9 and alpha of 0.05, a sample size of 40 per study arm has a power of 0.93 to detect a mean difference of 7 units. Assuming a PAP non-adherence rate and/or loss to follow-up of 40%, we will continue to have sufficient power (81%) to detect such a difference with our proposed sample size of 100. These findings would be in keeping with PASAT values obtained in non-disabled patients with SDB vs. controls, and PASAT performance in other populations (e.g. multiple sclerosis, mild traumatic brain injury).

Planned analyses: We will score questionnaires while blind to PSG data and group allocation using instructions provided by the questionnaire developer. We will first examine continuous variables for normality. For those variables without a normal distribution, we will explore appropriate transformations in an attempt to achieve normality. Continuous variables will be summarized as means and SD, and categorical variables will be summarized as frequencies. Prevalence of poor SQ will be calculated as the proportion of individuals who complete the PSQI with a score of  $\geq 5$ .

Prevalence of insomnia will be calculated as the proportion of individuals who complete the AIS with a score  $\geq 6$ . Prevalence of SDB will be calculated as the proportion of individuals who undergo PSG with AHI  $\geq 10/\text{hr}$ .

To determine baseline associations between SDB and cognitive measures (Hypothesis 1a), we will develop Generalized linear models (GLM), with each of the cognitive variables as dependent variables and presence or absence of SDB as an independent variable. The analyses will be repeated with AHI or ODI4 (measures of SDB severity) as independent variables. We will control for other co-variates including age, depression, anxiety, HRQOL, pain severity, duration of injury, level of injury, use of sedating medications, and presence of insomnia. For all GLM developed, the data may be transformed to meet the normality and homogeneity of variance assumptions of the analysis.

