**Last updated November 25, 2019**

## Background

Spinal cord injury (SCI) is universally recognized as a catastrophic disability impacting every aspect of life. The incidence of SCI within the US military is currently 429 per million person years, significantly higher than the civilian population. Disability from SCI exerts significant emotional, personal, economic, and social burdens. Most people with SCI sustain their injuries in their third or fourth decade of life, and lifespan after SCI remains significantly foreshortened. Medical co-morbidities including cardiovascular disease (CVD) have emerged as leading causes of mortality in chronic SCI with a prevalence exceeding non-disabled individuals, and an accelerated trajectory in early life. Prevalence rates of asymptomatic and symptomatic CVD in SCI populations range from approximately 25% to more than 50%. In contrast, among age-matched non-disabled populations the prevalence of CVD is typically reported to be in the range of 5–10%.

In addition to medical complications, 10 - 60% of individuals with SCI experience co-morbid cognitive impairments in the areas of processing speed, attention, memory, and cognitive flexibility. Cognitive impairments prolong near-term and chronic adjustment to disability, and delay learning of new skills. An emerging clinical challenge is the management of these medical, psychological and cognitive long-term sequelae of SCI.

An area that has garnered little attention in the SCI arena is the role of sleep disorders on psychological, cognitive, and physical health. People with SCI report higher rates of subjective sleep disturbances than the general population, particularly restless sleep, early morning awakenings, muscle spasms, daytime sleepiness, and snoring. In the general population, sleep disorders, and poor sleep quality adversely impact CV health, mood, emotional well-being, cognition, and health-related quality of life (HRQOL). In particular, sleep disordered breathing (SDB), characterized by periods of complete cessation of breathing (apnea) or marked reductions in airflow (hypopnea), sleep fragmentation, and frequent oxygen desaturations, is associated with impaired cognition, depression, greater susceptibility to pain, increased risk of stroke, hypertension, atrial fibrillation, diabetes, and perhaps even mortality in the general population.

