**Figure 1. Proposed Mechanisms for Cardiovascular Disease in Sleep Apnea**

PAP has been shown to improve some but not all cognitive deficits noted in persons with sleep apnea in the general population. Several studies have shown that post PAP therapy, cognition has improved in the areas of memory, sustained attention, motor speed, and executive function. However, other studies suggest no or minimal improvement in a battery of cognitive measures. Studies in this area are heterogeneous and vary by population characteristics, methodology, design, severity of SDB, duration of PAP prescription, and compliance with therapy. One hypothesis that has emerged from these conflicting reports on PAP and cognition is that PAP only partially reverses measured cognitive deficits. The reasons for this partial reversibility is not entirely clear but may be due to the lack of sensitivity of existing cognitive measures and/or structural changes in the brain that are no longer reversible. **Arguably individuals with chronic SCI differ from the general population in their medical co-morbidities contributing to cognitive decline as well as their baseline neuro-psychological vulnerabilities.** The treatment of SDB in this unique population may have a significant beneficial impact on cognitive function. Indeed there is limited evidence in the literature that suggests in other conditions with baseline cognitive deficits, treatment of SDB may lead to some improvement in cognitive performance. In a randomized trial of PAP treatment in mild Alzheimer's disease, following 3 weeks of PAP treatment, general cognitive performance improved within a subset of patients with Alzheimer's and sleep apnea. Subsequent analysis suggested those

with Alzheimer's and SDB who were adherent to PAP had a slower cognitive decline, especially in the domain of executive function and processing speed, exhibited stabilization of depressive symptoms and daytime somnolence, and showed significant improvement in subjective sleep quality. **Our proposal is the first to evaluate the impact of PAP therapy on cognitive measures in chronic SCI.**

*E) Impact of PAP on Cardiovascular Measures in the General Population*

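### The power statement takes a 7-point PASAT gap between populations as the PAP-versus-sham effect without justification, and its 81% does not reproduce

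*Combined protocol and SAP*

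**What the plan says.** The sample size paragraph under Data Analysis introduces the 7 points as follows: "A mean difference in PASAT scores of 7 discriminates between those with and without cognitive impairment in populations with and without SDB". It continues with "Assuming a standard deviation of 9" and states that "a sample size of 40 per study arm has a power of 0.93 to detect a mean difference of 7 units". Allowing 40% for non-adherence, loss to follow-up or both, it claims 81% power from the 100 participants randomised. It supports the target by comparison with "PASAT values obtained in non-disabled patients with SDB vs. controls" and with PASAT results in other conditions.

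The primary test (Data Analysis, Primary Hypothesis) is a different contrast: PAP against sham, one-sided at 0.05. Everyone in it has sleep disordered breathing, because randomisation requires an AHI of at least 10 (Randomization Protocol).

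On what PAP does to cognition, Background section D reports improvement in some domains, little or none in other studies, and the hypothesis that "PAP only partially reverses measured cognitive deficits".

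**The concern.** The 7 points describe how far apart two kinds of people are: impaired and unimpaired, or patients with the disorder and controls. The trial estimates how far PAP moves people who all have the disorder, relative to sham. The two coincide only if PAP, over sham, removes the whole cited gap on average. The plan gives no PASAT effect of PAP from any trial or before-and-after study. The background mentions the team's own cognitive data with PAP in acute SCI, but reports no figure and the power paragraph does not use them. Nor is 7 put forward as a minimal important treatment difference.

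What is at stake is how a non-significant result would be read. The Primary Hypothesis section plans confidence limits for the treatment difference only if the null is rejected. After a null result, the stated power would therefore be the main guide to what the trial had excluded. Readers told of 81% to 93% power could take partial benefit to be excluded when the trial could easily have missed it.

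**Working it through.** **Inputs.** Difference 7, SD 9, alpha 0.05, 40 per arm, 40% non-adherence or loss, 100 randomised (sample size paragraph); 1:1 allocation, so 50 per arm (Randomization Protocol); one-sided test (Primary Hypothesis). The power statement does not give its sidedness.

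**Formula.** Two-sample t test with n per arm: SE = SD × √(2/n), noncentrality = difference / SE, df = 2n − 2. Power is the probability that a noncentral t exceeds the critical value.

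**The stated 0.93.** SE = 9 × √(2/40) = 2.012; noncentrality = 7 / 2.012 = 3.478; df = 78.
- Two-sided, critical value 1.991: power 0.930. This reproduces the plan.
- One-sided, critical value 1.665: power 0.964.

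So 0.93 is a two-sided figure, although the planned test is one-sided.

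**The stated 81%.** 100 less 40% leaves 60, or 30 per arm. SE = 9 × √(2/30) = 2.324; noncentrality = 7 / 2.324 = 3.012; df = 58.
- Two-sided, critical value 2.002: power 0.842 (normal approximation 0.854).
- One-sided, critical value 1.672: power 0.909.

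Neither is 81%. Taking 40% off the 40 per arm leaves 24, which gives 0.751 two-sided and 0.844 one-sided. About 27 or 28 per arm does give it two-sided (0.801 and 0.815), but that is not 60% of 100. At 30 per arm the stated figure is about 3 points too low, so this slip is conservative.

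**Power if the true effect is smaller than 7.** The documents supply no treatment effect, so the range is an assumption. 3.5 is half the gap. 4.2 is 60% of it, which is also what remains of 7 if 40% of the PAP arm stay in the intention-to-treat analysis and gain nothing. Planned one-sided test at 0.05, SD 9:

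| True difference | 50 per arm | 40 per arm | 30 per arm |
|---|---|---|---|
| 7 | 0.987 | 0.964 | 0.909 |
| 5 | 0.867 | 0.793 | 0.685 |
| 4.2 | 0.749 | 0.664 | 0.556 |
| 3.5 | 0.613 | 0.532 | 0.438 |
| 2 | 0.294 | 0.255 | 0.214 |

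**Difference detectable with 80% power**, same method:

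| Test | 50 per arm | 40 per arm | 30 per arm |
|---|---|---|---|
| One-sided | 4.5 | 5.05 | 5.85 |
| Two-sided | 5.1 | 5.7 | 6.6 |

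**The case against.** The strongest reply is that the plan claims only the power to detect 7 points, and for 7 points the 0.93 is right. Powering for a target difference is accepted practice, and a gap that separates impaired from unimpaired people can be offered as a reason to regard 7 as meaningful. That stands as far as the arithmetic goes. It does not supply the missing step, because the text never calls 7 a target or argues that it is the treatment difference that matters.

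The reply also has force on the evidence. Partial reversal is presented as one hypothesis, drawn from general-population studies. The same section cites cognitive gains with PAP and argues that people with chronic SCI may benefit more. So the documents do not show that the effect must fall below 7; they give no figure either way.

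Adjustment could also help. With baseline PASAT in the model and an assumed correlation of 0.7, the residual SD is 9 × √(1 − 0.49) = 6.43, and one-sided power for 3.5 points with 50 per arm is about 0.86 (normal approximation). But baseline PASAT is not among the listed covariates, and the power statement claims no such gain.

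Two stronger readings are tempting, and the documents support neither.
- A reader might call 7 an upper bound on the PAP effect. The figure is referenced to non-disabled patients, and Background section B suggests that sleep disordered breathing may add to deficits already present in SCI, so the gap in this population could be larger.
- A reader might note that "10 - 60% of individuals with SCI experience co-morbid cognitive impairments", multiply 7 by that share to get 0.7 to 4.2 points, and quote power of 0.06 to 0.54 (40 per arm, two-sided). That share is for SCI in general and across several cognitive areas; it is not a PASAT impairment rate in SCI with sleep disordered breathing. If the 7 is a patient-versus-control difference, it already averages over impaired and unimpaired patients, and the multiplication discounts twice.

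**Conclusion.** The concern holds as a fault in the justification of the effect size. The 7 points are a between-population gap used as the treatment difference, with no PAP-versus-sham evidence and no argument that 7 is a minimal important difference. The 0.93 is correct for a true difference of 7 (two-sided, 40 per arm). The 81% does not reproduce at 30 per arm: it should be 0.842 two-sided or 0.909 for the planned one-sided test.

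The trial is well powered for 7 points even at 30 per arm. For half that difference, one-sided power is between 0.44 and 0.61. These figures rest on SD 9, on the t test without covariate gain, and on effect sizes chosen for illustration. A reader might infer that the trial is known to be underpowered; the documents do not establish that, because they contain no estimate of the effect from which to measure a shortfall.

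**What to change.** In the sample size paragraph:

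1. Say that 7 is a between-population gap, or justify it as a target important difference for PAP over sham.
2. Replace the 0.93 and 81% figures with power for the planned one-sided 0.05 test at SD 9, for differences of 7, 5, 4.2, 3.5 and 2 at 50, 40 and 30 per arm (first table above), labelled as an assumed range.
3. State the 80%-power detectable differences: 4.5, 5.05 and 5.85 one-sided, and 5.1, 5.7 and 6.6 two-sided.
4. Add a sentence that a non-significant result does not exclude smaller effects.

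The sample size, the primary test and trial conduct do not change, and this point calls for no treatment-by-baseline interaction analysis, which would have low power here. The cost is a wording amendment and a stated power that looks less favourable for effects below 7.
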